Data Collection: Data collection will include age, race, gender, BMI, data for calculating an APACHE II and SOFA scores, suspected source of infection, identified pathogens, pre-existing conditions that may predispose the patient to AF and the severity/classification of such illness (coronary artery disease, heart failure, chronic kidney disease, chronic obstructive pulmonary disease, diabetes mellitus); vital signs at the onset of AF (mean arterial pressure, systolic blood pressure, heart rate), lactate, pH, and serum bicarbonate at the time of AF onset; fluid resuscitation volume for the 24 hours prior to AF, vasopressor use (including drug, dose, duration) in the preceding 24 hours; other medications used to stabilize hemodynamic status in AF (e.g. β-blockers, calcium channel blockers, digoxin), other attempted methods of cardioversion attempted prior to amiodarone use (e.g. direct current cardioversion, other antiarrhythmic drug therapy); amiodarone loading dose, cumulative study amiodarone dose; the duration of time spent in AF before conversion to NSR, the incidence of AF recurrence; and hemodynamic variables to be assessed at various time points after the initiation of amiodarone (-6 hours, at onset of AF, 2 hours, 6 hours, 12 hours, and every 6 hours thereafter until day 7 or death)

including mean arterial pressure, central venous pressure, systolic blood pressure, heart rate, pH, serum bicarbonate, and serum lactate.

Monitoring for Efficacy and Safety:

Efficacy: Patients will be stratified based on response to therapy into one of three groups: conversion to NSR, nonconverting AF that is hemodynamically stable or non-converting AF that is hemodynamically unstable. The primary efficacy outcome is the mean heart rate every 6 hours after initiation of the amiodarone infusion to day 7 or death. Secondary efficacy endpoints will include the percentage of time spent hemodynamically unstable in the first 7 days following amiodarone initiation, intensive care unit length of stay (LOS), hospital LOS and 28-day mortality along with comparisons of the individual portions of the hemodynamic endpoints (MAP, HR, SBP), cumulative vasopressor doses of norepinephrine and vasopressin, CVP, conversion to NSR, maintenance of NSR, proportion of time spent in NSR after the start of the infusion to day 7 or death, pH, standard bicarbonate, serum lactate, and central venous oxygen saturation.

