Safety: Safety outcomes include worsening of hypotension (largely related to the rate of infusion and the polysorbate 80 diluent), bradycardia, acute elevations of liver function tests ≥ 3 times the upper limit of normal, phlebitis, QTc prolongation, skin reactions, neuropathy, and pulmonary toxicity. We will also collect premature study discontinuation due to any adverse event. Because the experimental group of this study is a partial load of amiodarone, rather than a full load, it is likely that the experimental group will experience fewer amiodarone related adverse effects than those receiving the current practice. In the setting of worsening hemodynamic stability during amiodarone infusion (i.e. SBP <90 mmHg OR MAP < 70 mmHg, despite HR control of < 120 bpm; need for fluid boluses ± vasopressors or dobutamine), which the medical team believes to be caused by IV amiodarone therapy:

- 1. the amiodarone infusion rate should be decreased by 50%, with efforts to increase back to the standard infusion rate after the patient is hemodynamically stable, *or*
- 2. switch from IV amiodarone to PO amiodarone therapy at a dose of 400 mg PO TID, or
- 3. emergent electro-cardioversion at the discretion of the medical team (as is the standard of care)

Data Analysis Plan: Data will be collected and stored using Microsoft Excel or Access. After data organization and cleaning, data will be imported into JMP 12.0 or SPSS. Data will be analyzed using both descriptive and comparative statistics. The primary outcome will be analyzed using repeated measures ANOVA. Nominal and ordinal variables will be compared using Chi-square test or Fisher's Exact test, as appropriate. Continuous variables will be tested for normality using the Shapiro-Wilk W goodness of fit test. Continuous variables with normal distributions will be compared using the student's t-test, while non-parametric variables will be compared using the Wilcoxon rank sum test. Statistical significance will be defined as an alpha level less than 0.05.

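### Secondary blood-pressure, CVP and laboratory outcomes are read up to 28 times per patient but get single-value tests, with neither the single value nor a longitudinal model defined

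*Combined protocol and SAP*

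**What the plan says.** Item 6, Data Analysis Plan, names a method for serial data once: "The primary outcome will be analyzed using repeated measures ANOVA". The general rule for continuous variables follows: those with normal distributions go to Student's "t-test, while non-parametric variables will be compared using the Wilcoxon rank sum test". The threshold is given as "Statistical significance will be defined as an alpha level less than 0.05", with no multiplicity rule.

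Item 6, Data Collection, schedules readings at −6 hours, at AF onset, then "2 hours, 6 hours, 12 hours, and every 6 hours thereafter until day 7 or death", for hemodynamic variables "including mean arterial pressure, central venous pressure, systolic blood pressure, heart rate, pH, serum bicarbonate, and serum lactate".

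Item 6, Efficacy, makes these variables secondary endpoints. It calls for "comparisons of the individual portions of the hemodynamic endpoints (MAP, HR, SBP") and adds CVP, pH, bicarbonate, lactate and central venous oxygen saturation. Item 4 also lists MAP, SBP and HR as secondary outcomes, without a definition.

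Other secondary outcomes are already one number per patient: percentage of time unstable, proportion of time in sinus rhythm, cumulative vasopressor dose, and ICU and hospital length of stay. No such number is defined for MAP, SBP, CVP, pH, bicarbonate or lactate. The regression paragraph that follows the tests refers only to study outcomes in general and gives no structure for repeated readings.

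**The concern.** A t-test or rank sum test needs one independent value per patient. The plan recognises the serial structure of six-hourly heart rate but gives no such treatment to six other variables on the same schedule. An analyst must therefore decide, possibly after seeing the data, whether to test every time point, pool the readings or summarise each patient. The three choices have very different error rates.

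MAP and SBP matter in this trial. Item 6, Safety, lists worsening hypotension among the safety outcomes and uses SBP and MAP limits to describe hemodynamic worsening during the infusion. A false between-arm difference in blood pressure, or in lactate or pH, could colour the comparison of the two loading strategies.

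Heart rate adds an ambiguity. Six-hourly HR is the primary outcome under one method, and HR is also an undefined secondary outcome under the default rule.

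**Working it through.** **Plan's own figure.** The documents give none for these secondary analyses, so there is nothing to reproduce. The sample size (250 per group, 15% drop-out) concerns the primary outcome. It is used here only to set the simulated arm size: 250 × 0.85 = 212.5, taken as 212.

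**Inputs from the documents.** Six-hourly readings from 6 h to 168 h: 168 / 6 = 28. The 2 h reading makes 29, and the −6 h and AF-onset readings make 31. These are maxima, because collection stops at death. Serial secondary outcomes other than HR: 6 (MAP, SBP, CVP, pH, bicarbonate, lactate). Alpha is 0.05, taken as two-sided because the plan does not say.

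**Assumed.** The documents give no within-patient correlation. The range shown is a constant correlation ρ of 0.3 to 0.7, or AR(1) with ρ of 0.7 to 0.9.

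**Route 1, pooling all readings as independent.**
- Design effect (DE), constant correlation: DE = 1 + 27ρ.
- Design effect, AR(1): DE = 1 + 2 Σ(1 − k/28)ρ^k, for k = 1 to 27.
- Naive SE / true SE = 1/√DE.
- Actual type I error = 2 × (1 − Φ(1.96/√DE)).
- Example, ρ = 0.3: DE = 1 + 27 × 0.3 = 9.1; √9.1 = 3.02; 1.96/3.02 = 0.65; type I error = 52%.

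**Route 2, a t-test at each of the 28 times.** Each test holds 5%. If the tests were independent, the chance of at least one p < 0.05 with no true effect would be 1 − 0.95^28 = 76%. Correlation lowers this, so it was simulated.

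**Route 3, one mean per patient, then a t-test or Wilcoxon test.** Simulated.

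Simulations used normal data with no arm difference, 212 patients per arm, complete series of 28 and 2,000 runs.

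| Assumed correlation | DE | Naive SE / true SE | Pooled, formula | Pooled t, simulated | Any of 28 times, simulated | Patient mean, t / Wilcoxon |
|---|---|---|---|---|---|---|
| Constant 0.3 | 9.1 | 0.33 | 52% | 51.8% | 65.6% | 5.4% / 6.1% |
| Constant 0.5 | 14.5 | 0.26 | 61% | 61.7% | 49.7% | 4.8% / 5.0% |
| Constant 0.7 | 19.9 | 0.22 | 66% | 68.2% | 34.1% | 4.5% / 4.6% |
| AR(1) 0.7 | 5.1 | 0.44 | 39% | 37.6% | 62.7% | 4.7% / 4.8% |
| AR(1) 0.9 | 12.9 | 0.28 | 59% | 58.9% | 39.3% | 4.1% / 4.6% |

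A separate run of 100,000 simulations for route 2 gave 64%, 49% and 33% at constant correlations of 0.3, 0.5 and 0.7. Taken together, route 2 spans about 33–66% per variable and route 1 about 39–66% by formula. Even at ρ = 0.05, pooling gives DE = 1 + 27 × 0.05 = 2.35 and a type I error of 20%.

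Route 2 applied to all six outcomes means 6 × 28 = 168 tests.

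**The case against.** The best defence is that the rule is generic. It must also cover age, BMI and length of stay, and nothing in it says that every reading enters as a separate observation. The documents often think in per-patient quantities: the power paragraph speaks of a mean HR over 7 days, and several secondary endpoints are percentages or cumulative doses per patient. If MAP and lactate were reduced to a patient mean in the same way, the assigned tests would hold about 5%.

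That defence stands against a stronger claim that a reader might infer: that the plan's p-values for these outcomes are wrong. They would be wrong in that sense only under pooling, which the plan never states. Testing at each time point is a multiplicity problem, not a failure of each test. The defence does not close the gap, because the plan neither chooses the benign route nor excludes the other two.

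A reader might also infer that the HR readings are bound to give two conflicting answers. The documents do not support that. Item 4's definition of instability includes an HR threshold sustained for at least 2 hours, so the HR portion named under Efficacy may be a different quantity from the primary mean. The text is unclear, and that calls for a definition.

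Nor do the documents rank blood pressure as the main signal of harm. Worsening hypotension is one of several listed safety outcomes and may be recorded as an event.

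**Conclusion.** The point holds as an underspecified rule that allows misleading analyses, not as a demonstrated error. Six secondary outcomes with up to 28 six-hourly readings each are given tests that need one value per patient, and that value is not defined. Depending on the route taken, the false-positive rate per variable is about 5% (patient summary), about 33–66% for at least one false positive (each time point tested), or about 39–66% (pooled readings).

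The last two ranges depend on the assumed correlations and on complete 28-reading series. Deaths would shorten the series and change the figures. Item 3 cites mortality of 70–80% for new-onset AF in sepsis, so truncation by death cannot be ignored, and the plan does not say how truncated series are to be compared.

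Severity is moderate. The affected outcomes are secondary, the primary outcome has its own repeated-measures method, and a short amendment settles the matter.

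**What to change.** For MAP, SBP, CVP, pH, bicarbonate and lactate, replace the default t-test/Wilcoxon rule with one prespecified between-arm contrast per outcome:

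- **Preferred:** a linear mixed model with patient as random effect and with time, arm and the pre-amiodarone value as terms. Name the single contrast to be reported.
- **Alternative:** a time-weighted mean per patient, compared between arms with adjustment for the pre-amiodarone value.

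In either case, state which pre-amiodarone reading is the baseline (the schedule has one at −6 hours and one at AF onset) and how series cut short by death are handled. A time-weighted mean does not settle that by itself, because follow-up lengths will differ.

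Define secondary HR as a quantity different from the primary, or remove it. State how often central venous oxygen saturation is read: it is a secondary endpoint but is not among the variables listed on the serial schedule. Keep the t-test and Wilcoxon test for variables with one value per patient.

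The cost is a few sentences in the plan and a little more analysis work, with no new data. Compared with pooling or time-by-time testing, fewer secondary results will be nominally significant. Some multiplicity across outcomes remains: six independent contrasts at 0.05 give 1 − 0.95^6 = 26% for at least one false positive, so these results should be labelled supportive.

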Intervention: Patients aged 18 years or older who develop new-onset atrial fibrillation in the setting of severe sepsis or septic shock and in whom the medical team deems appropriate to initiate amiodarone therapy in will be considered for study inclusion. All patients will receive a 150 mg intravenous (IV) bolus dose of amiodarone, followed immediately by a continuous infusion of 1 mg/min for the first six hours, with a recommended reduction to 0.5 mg/min subsequently. Conversion from IV to oral (PO) amiodarone will occur based on patient hemodynamic stability and physician/pharmacist discretion. Patients will be randomized to receive amiodarone at a full loading dose (\geq 5g IV or \geq 10g PO +/- 20%) or a partial loading dose (<4g IV or < 8g PO). The assigned total loading dose will include all IV and PO amiodarone administered within 7 days from initiation of amiodarone. All doses will be compared in total PO amount (accounting for 50% bioavailability of PO versus IV amiodarone). The primary attending or fellow physician may over-ride randomization if the patient's amiodarone dose if the patient's severity of illness warrants a duration that differs from that assigned during randomization. In the full loading dose group, discontinuation of amiodarone will be at the discretion of the physician/pharmacists, after the pre-determined randomization loading dose has been provided.

Management Components: Facilities to be used throughout the project include the University Hospital and The University of Texas Health Science Center at San Antonio. Equipment use for direct patient care will be in keeping with standards-of-care, without any additional equipment being required for the clinical research study.

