All baseline demographics, including patient comorbidities, amount of fluid resuscitation, previous vasoactive therapies, and use of other interventions such as direct current cardioversion, will be entered into a multivariate regression model if the p value is less than 0.20 on univariate comparison between treatment groups. The multivariate regression model will be used to assess if baseline factors or previous treatment other than the intervention affected the study outcomes.

Based on extrapolation from available literature assessing HR control at 24 hours, we estimate that the full loading dose group will have a mean HR of 110 bpm over the course of 7 days, while the partial loading dose group will have a mean HR of 130 bpm over the course of 7 days. 7 day mean HR that is 20 bpm lower than the partial loading dose group. Therefore, we estimate that 250 patients will be necessary in each group to have an 85% power to detect a difference, assuming a 15% drop-out rate.

Item 7 Risks Section:

Complete the following table to describe the risks of all research procedures listed in Step 2, Institutional Form (items 28-34). Do not list risks of Routine care procedures here.

isks are described in the informed consent document – do not complete this table.

Research procedures	Risks
 example: History and physical Questionnaire Laboratory tests 	List the reasonably expected risks under the following categories as appropriate:
Add or delete rows as needed

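### The regression admits baseline factors by a between-arm p<0.20 screen that ignores prognostic strength, and the primary model names no baseline heart rate covariate

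*Combined protocol and SAP*

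**What the plan says.** Item 6, Data Analysis Plan, lists candidate factors (demographics, comorbidities, fluid volume, earlier vasoactive treatment, other interventions) that "will be entered into a multivariate regression model if the p value is less than 0.20 on univariate comparison between treatment groups". The next sentence says the model will be "used to assess if baseline factors or previous treatment other than the intervention affected the study outcomes". No factor is selected for its relation to outcome and none is forced in. The plan does not say which outcomes the model covers or what type of regression it is.

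The primary analysis gets one sentence: "The primary outcome will be analyzed using repeated measures ANOVA". No covariate is named. Item 6, Efficacy, defines the endpoint after treatment starts: "The primary efficacy outcome is the mean heart rate every 6 hours after initiation of the amiodarone infusion to day 7 or death".

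Item 6, Data Collection, records "vital signs at the onset of AF (mean arterial pressure, systolic blood pressure, heart rate". It also puts pre-treatment and follow-up readings in one series; its time points, the first of which carries a minus sign, are "6 hours, at onset of AF, 2 hours, 6 hours, 12 hours, and every 6 hours thereafter until day 7 or death". The plan does not say how the pre-treatment readings enter the model.

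Two other statements matter. Item 6, Intervention, says "The primary attending or fellow physician may over-ride randomization", and no analysis population is defined. The sample size paragraph says "250 patients will be necessary in each group to have an 85% power to detect a difference, assuming a 15% drop-out rate", for means of 110 and 130 bpm, without a standard deviation.

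**The concern.** The main point is a mismatch between purpose and entry rule. Whether a factor affected the outcome is a question about factor and outcome; the screen looks at factor and treatment arm. In a randomised comparison the second says nothing about the first. A strong predictor is usually excluded because the arms happen to be similar on it, and a factor unrelated to outcome is admitted one time in five. A factor that does enter has its association estimated properly, so the fault lies in the entry rule and not in the regression. The covariate list is also unknown until the data are seen.

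The secondary point concerns precision. Baseline heart rate is an obvious candidate covariate for a heart rate endpoint and costs nothing to use. Because the data collection list runs pre-treatment and follow-up readings together, the plan should also state that the AF-onset value is a covariate and not one of the repeated outcomes.

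**Working it through.** **Inputs.** From Item 6: 250 per group, 15% drop-out, 85% power, a difference of 130 − 110 = 20 bpm, alpha 0.05 (two-sided assumed), entry threshold 0.20. The documents give neither the SD of heart rate nor the correlation r between a baseline factor and the outcome, so both are varied. Evaluable patients per arm: 250 × 0.85 = 212.5, taken as 212.

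**The plan's own figure.** Without an SD, 250 per group cannot be reproduced forwards. Solved backwards by the normal approximation, SD = 20 × √(212.5/2) / (1.960 + 1.036) = 68.8 bpm; the noncentral t with 212 per arm gives 68.6. That is very large: 110 − 2 × 68.6 = −27 and 130 − 2 × 68.6 = −7. It serves here as an upper end.

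**Entry under the screen.** With chance imbalance only, the between-arm p value is uniform, so P(p < 0.20) = 0.20; r does not appear. Simulation: y = r·x + √(1 − r²)·e, normal x and e, no treatment effect, 212 per arm, 40,000 trials per r; x is admitted if its between-arm t-test gives p < 0.20.

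| r | Factor enters | Type I error, screen then adjust |
|---|---|---|
| 0 | 20.0% | 5.0% |
| 0.1 | 19.8% | 4.9% |
| 0.2 | 20.1% | 4.7% |
| 0.3 | 19.6% | 4.4% |
| 0.5 | 20.2% | 3.7% |

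The rule is conservative, not liberal.

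**Spread of the treatment estimate relative to unadjusted.** Always adjusting: 0.955 at r = 0.3 and 0.867 at r = 0.5. Screen: 0.971 and 0.914. The screen therefore gives up part of the available gain.

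**Read as a check on chance confounding.** An imbalance just missing p < 0.20 is at most t(0.90, 422 df) = 1.284 standard errors, which shifts the treatment difference by up to 1.284·r SE, uncorrected. At an assumed SD of 40, SE = 40 × √(2/212) = 3.885 bpm.

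- r = 0.3: 1.284 × 0.3 = 0.385 SE, or 1.50 bpm
- r = 0.5: 1.284 × 0.5 = 0.642 SE, or 2.49 bpm

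These are maxima. The mean absolute imbalance among factors that fail the screen is 2(φ(0) − φ(1.2816))/0.8 = 2(0.3989 − 0.1755)/0.8 = 0.559 SE. The typical shift is then 0.559 × 0.3 × 3.885 = 0.65 bpm at r = 0.3 and 0.559 × 0.5 × 3.885 = 1.1 bpm at r = 0.5.

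**Baseline heart rate in the primary model.** For a group comparison of one 7-day mean per patient with complete data, the interval narrows by 1 − √(1 − r²): 0.5%, 2.0%, 4.6% and 13.4% at r = 0.1, 0.2, 0.3 and 0.5. Power for 20 bpm, using residual SD = SD × √(1 − r²):

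| SD (bpm) | Unadjusted | r = 0.3 | r = 0.5 |
|---|---|---|---|
| 50 | 98.4% | 99.1% | 99.7% |
| 60 | 92.8% | 94.8% | 97.7% |
| 68.6 | 85.0% | 88.1% | 93.3% |

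At SD 40 or less, power is already 99.9% or more and hardly moves. At SD 68.6 the smaller correlations give 85.3% (r = 0.1) and 86.4% (r = 0.2). These figures do not carry over to a group-by-time test.

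**The case against.** The stakes are modest, and that stands. The unadjusted comparison is valid and no error rate is inflated. Replacing the screen moves the cut in spread only from 2.9% to 4.5% at r = 0.3. The bpm shifts at the p = 0.20 boundary are worst cases; typical values are under half of them.

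A between-arm screen is perhaps most naturally read as a check on confounding by imbalance, in which case an excluded factor is simply one without marked imbalance. That reading is fair, and it narrows the criticism without removing it: the harm from an imbalance depends on its size multiplied by the factor's prognostic strength, and the screen sees only the first.

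The 20% entry rate needs analysis as randomised and a factor fixed before randomisation. With override allowed and no analysis population stated, the first is not assured. Some candidates, such as cardioversion, could also occur after randomisation. If patients were analysed by dose received, imbalance would not be pure chance and 20% would not apply, but prognostic strength would still be ignored.

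On baseline heart rate, the endpoint definition already points to post-initiation readings as the outcomes, so that part of the remedy is mostly clarification. The gain may also be small: Item 3 cites a fall from 150 to 104 bpm within 2 hours of amiodarone, so AF-onset heart rate may predict the 7-day mean only weakly.

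**Conclusion.** The concern holds as a free improvement, not as a threat to validity. Analysed as randomised, any given baseline factor, strong predictor or not, is absent from the regression in about 80% of trials, so the model often cannot answer the question set for it. Pre-specified prognostic covariates serve either reading of its purpose better. Omitting baseline heart rate from the primary model costs precision only: from almost nothing (r = 0.1, or SD of 40 or less) to about 8 points of power (93.3 − 85.0 = 8.3) at r = 0.5 and the implausibly large SD implied by the sample size. Confidence in the size is medium, because every r and SD is an assumption. The mismatch in the entry rule depends on neither.

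**What to change.** Delete the p<0.20 screen. Name a short list of regression covariates in advance on prognostic grounds and keep them whatever the between-arm p values. Item 6, Data Collection, already supplies candidates, for example APACHE II or SOFA score, lactate at AF onset and vasopressor use in the preceding 24 hours; the choice is for the investigators. Restrict the list to values fixed before randomisation, and state the outcomes and type of regression the model covers.

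For the primary analysis, enter heart rate at AF onset as a fixed covariate in the repeated-measures model, and state that only post-initiation readings are outcomes.

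The cost is a few sentences of analysis text, with no added patients, visits or measurements. It should be settled before outcome data by arm are seen.

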successful cardioversion with amiodarone in general is approximately 75% within the first 24 hours.(12

Kanji and colleagues noted successful conversion to NSR was achieved in 50% of a mixed medicalsurgical patient population that underwent DCC, though 73% reverted back to AF. Successful conversion to NSR was obtained in 87% of patients receiving amiodarone, some of whom also underwent DCC, though 42% reverted back to AF at some time during their ICU stay after maintaining normal sinus rhythm for at least 24 hours after conversion. The median duration of amiodarone therapy was 4 days (range 1-49) and a median cumulative intravenous dose of 2324 mg (range 150-20550 mg).(5) Clemo and colleagues found that in a mixed ICU population, within 2 hours of amiodarone initiation, aimed at an intravenous loading dose of 2-3 mg/kg, there were significant reductions in heart rate from 150 bpm to 104 bpm and increases in systolic blood pressure from 90 mmHg to 118 mmHg. Within 24 hours, 76% of patients had successfully converted to NSR, which was maintained in 52% of patients with an average cumulative intravenous dose of 2035 ± 1962 mg and an average duration of amiodarone treatment of 84 ± 79 hours.(13) Faneil and colleagues found that in a mixed ICU setting, patients refractory to DCC or other antiarrhythmic agents, amiodarone achieved successful conversion to NSR in 80.8% of patients in an average of 171 minutes. They noted that maintenance of NSR required an average amiodarone dose of 6.9 ± 2.3 mg/kg.(14) In a recent systematic review by Kanji and colleagues, they found that no study evaluated the maintenance of conversion to NSR(6).

- 1. Rivers EP. Early and innovative interventions for severe sepsis and septic shock: taking advantage of a window of opportunity. Can Med Assoc J. 2005;173(9):1054–1065.
- 2. Christian S-A, Schorr C, Ferchau L, Jarbrink ME, Parrillo JE, Gerber DR. Clinical characteristics and outcomes of septic patients with new-onset atrial fibrillation. J Crit Care. 2008;23(4):532–536.

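### The planned 20 bpm difference in 7-day mean heart rate rests on unidentified 24-hour data, although both arms have the same written dosing to 24 h, and it does not fit 250 per group at 85% power unless the SD is about 69 bpm

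*Combined protocol and SAP*

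**What the plan says.** Item 6, sample size paragraph: the assumed effect is introduced as "Based on extrapolation from available literature assessing HR control at 24 hours". It continues: "we estimate that the full loading dose group will have a mean HR of 110 bpm over the course of 7 days", against 130 bpm in the partial loading dose group. It concludes that "250 patients will be necessary in each group to have an 85% power to detect a difference", allowing for 15% drop-out. No SD, within-patient correlation, sidedness, formula or literature reference is given there.

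Item 6, Intervention: every patient receives a 150 mg IV bolus, "followed immediately by a continuous infusion of 1 mg/min for the first six hours, with a recommended reduction to 0.5 mg/min subsequently". The arms are defined by cumulative dose: "The assigned total loading dose will include all IV and PO amiodarone administered within 7 days from initiation of amiodarone".

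Item 6, Efficacy: "The primary efficacy outcome is the mean heart rate every 6 hours after initiation of the amiodarone infusion to day 7 or death".

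Item 6, Data Analysis Plan: "The primary outcome will be analyzed using repeated measures ANOVA", with alpha 0.05 and no statement of one- or two-sided testing.

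Item 3, Background: the only quantified heart-rate result is that within 2 hours of starting amiodarone "there were significant reductions in heart rate from 150 bpm to 104 bpm".

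**The concern.** The effect and the power are the plan's only statement of what the trial can detect, and each has a problem.

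First, the effect is a 7-day contrast between two loading doses, but its stated basis is heart rate at 24 hours. At 24 hours the written regimen does not yet distinguish the arms. The primary endpoint averages from initiation, so it also includes this shared period.

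Second, 250 per group looks far too many for a 20 bpm difference in a patient-level average. Either the SD, the effect or the sample size is not what was intended, and the reader cannot tell which. A null or small result could not be interpreted against such a power statement.

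**Working it through.** **Inputs from the documents.** Means 110 and 130 bpm, so a difference of 20 bpm; 250 per group; 15% drop-out; 85% power (Item 6, sample size paragraph). Alpha 0.05 (Data Analysis Plan). Bolus 150 mg, then 1 mg/min (60 mg/h) for 6 h, then 0.5 mg/min (30 mg/h) (Intervention).

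**Assumptions.** Two-sided test, normal approximation, comparison of patient-level 7-day means (the quantity in which the effect is stated). The documents give no SD, so 15 to 30 bpm is an assumed range.

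**1. Can 250 be reproduced?** Not from stated inputs, because the SD is missing. Solve for it instead.

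- Evaluable per arm: 250 × 0.85 = 212.5, taken as 212.
- z(0.975) + z(0.85) = 2.996; √(2/212) = 0.0971.
- Implied SD = 20 / (2.996 × 0.0971) = 68.7 bpm.

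Other per-group readings: one-sided, 76.8 bpm; two-sided with drop-out ignored, 74.6; one-sided with drop-out ignored, 83.4. Using a t-test gives 68.6.

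**2. Is that spread plausible?** Around the planned midpoint of 120 bpm, one SD either side is 51 to 189 bpm. Two SDs below is 120 − 2 × 69 = −18 bpm. Repeated measures do not rescue the figure: 69 bpm is the SD of an average, and the SD of a single reading would be at least as large.

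**3. What 20 bpm would need.** n evaluable = 2 × (2.996 × SD / 20)², rounded up, then divided by 0.85. The detectable difference is 2.996 × 0.0971 × SD.

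| Assumed SD (bpm) | Evaluable per group | Enrolled per group | Power for 20 bpm at 212 | Difference detectable at 85% with 212 |
|---|---|---|---|---|
| 15 | 11 | 13 | >99.9% | 4.4 bpm |
| 20 | 18 | 22 | >99.9% | 5.8 bpm |
| 25 | 29 | 35 | >99.9% | 7.3 bpm |
| 30 | 41 | 49 | >99.9% | 8.7 bpm |

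Even at an SD of 40 bpm the requirement is 85 enrolled per group, and power with 212 evaluable is still above 99.9%.

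**4. Dose at 24 h on the written IV rates.** 150 + 60 × 6 + 30 × 18 = 150 + 360 + 540 = 1,050 mg, with no arm-specific term.

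**5. What a 7-day average of 20 bpm requires.** If there is no difference until hour t and a constant one afterwards, with complete data, that later difference must be 20 × 168 / (168 − t). For t = 24 h this is 20 × 168 / 144 = 23.3 bpm. It rises with later divergence. At the boundary where both arms run on IV rates to 4 g, t = (4,000 − 510)/30 + 6 = 122.3 h, and it is about 74 bpm. That is a limit and not a forecast, since the partial arm has no minimum dose and may stop much earlier.

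**6. What the cited data compare.** The 150 to 104 bpm result is a before-after change. The mean cumulative IV dose in that study, 2,035 mg, lies within this trial's partial-load range, so the result does not point to 130 bpm in the partial arm. The Background reports no comparison of two amiodarone loading doses.

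**The case against.** The strongest replies are these.

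- *The plan calls its basis an extrapolation and says that dosing data are limited.* True. Because the literature is not identified, it cannot be said that the effect has no support, only that support is not shown.
- *Patients may differ before 24 h.* The step-down is only recommended, the oral switch is discretionary and physicians may override randomisation. So 1,050 mg describes the written rates and not every patient. None of these departures has arm-specific timing in the text, however, so none of them supplies the missing link.
- *Sidedness is unstated, so 69 bpm is not the only solution.* Accepted. The one-sided readings, about 77 to 83 bpm, are less plausible still.
- *The SDs of 15 to 30 bpm have no source.* Accepted; they are labelled as assumptions. The conclusion does not depend on the exact value, as the SD 40 case shows.
- *Enrolling more patients than 20 bpm needs is not a validity defect.* Correct. The defect is in the stated power.

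A reader might also infer that the shared early period dilutes 20 bpm to a much smaller 7-day difference and costs power. The documents do not support this. The sample size paragraph defines 110 and 130 bpm as means over the 7 days, so early readings are already inside the 20 bpm. The shared period instead raises the difference that the later days must supply. Nor does the detectable 7-day difference depend on when the arms diverge.

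**Conclusion.** The point holds in two parts. The documents do not show support for a 20 bpm between-dose difference in 7-day mean heart rate. The source is unidentified, concerns 24 hours, and is applied to arms with the same written dosing up to that time. With no difference on day 1, the remaining six days would have to supply about 23 bpm, and more if divergence is later.

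Separately, 20 bpm, 250 per group, 15% drop-out and 85% power do not fit together at any plausible spread. They require an SD of about 69 bpm two-sided (about 77 to 83 one-sided). At assumed SDs of 15 to 30 bpm the planned effect needs 13 to 49 per group, against the 250 planned.

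A reader might infer from this that the trial is underpowered. That is not shown: at those SDs, 250 per group has 85% power for differences well below 20 bpm. What is wrong is the power figure for the stated effect. This should be fixed, but it does not undermine the primary endpoint or the enrolment target.

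**What to change.** Keep 250 per group and the 7-day primary endpoint.

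1. Restate the sample size paragraph with the SD of a patient's 7-day mean, its source, and the sidedness. For example: *With 250 per group and 15% drop-out, the trial has 85% power (two-sided 0.05) to detect a difference in 7-day mean heart rate of 4.4, 5.8, 7.3 or 8.7 bpm if the SD is 15, 20, 25 or 30 bpm.* Use the sourced SD once it is available.
2. Replace the 24-hour extrapolation with a justification that takes account of the shared early period and identifies its literature. Otherwise, state that 20 bpm is not supported by between-dose data.
3. Optionally, prespecify from the same repeated-measures model a supportive as-randomised arm contrast over fixed late clock times from initiation, identical in both arms and chosen before data are seen. This would be an addition, since the plan names no analysis population. Its downside is fewer readings (12 of the 28 six-hourly readings fall after 96 h) and the loss of patients who die earlier. The Background cites 70-80% mortality without its timing, so the contrast should stay supportive.

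The cost is revised wording, a recalculation, and the work of finding a sourced SD and a defensible difference, neither of which is in the documents. No extra data collection on trial patients is needed, and no dose or clinical rule is proposed.
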